Patients will be anesthetized with 3% Mepivacaine with 1:100,000 epinephrine (Mepiadre, DFL, RJ, Brazil), and the teeth will be isolated with a rubber dam (Madeitex, São José dos Campos, Brazil). The operative field will then be disinfected with a povidone-iodine solution. After coronary accesses, the root canals will be prepared to #35/0.04 reciprocating instrument (Blue S-one, Fanta Dental, Shanghai, China). All root canals will receive irrigation with 2.5% sodium hypochlorite, with a syringe (Descarpack, São Paulo, Brazil) and irrigation needle (Navitip, Ultradent, Utah, USA). At the end of preparation, each canal will receive the following final irrigation protocol: 10 ml of sodium hypochlorite, with 30-second activation (PUI) with an E1 ultrasonic insert (Helse, Santa Rosa do Viterbo, SP, Brazil), coupled to an ultrasound device (PM 200, EMS, Switzerland) at 10% power. Second activation with 10 ml of EDTA-T (Fórmula &

Ação, São Paulo, Brazil) for 30 seconds with the same parameters. Third activation with 10 ml of sodium hypochlorite for 30 seconds with the same parameters.

There will be no questionnaire.

Laser Ablation Protocol

After chemo-mechanical preparation, all root canals of all patients assigned to the trial intevention will receive laser ablation (LA) therapy with the indocyanine green solution (ICG). First, the root canals will be filled with 0.05% ICG solution (MP Biomedicals - Thermo Fisher Scientific, Pittsburgh, PA) which will remain in the root canal for 1 minute (pre-irradiation time). After this period, a #20 laser fiber will be inserted into the root canals to the working length. Then, 810 nm wavelength infrared diode laser (Leonardo, CAO Group, West Jordan-UT) will be activated with a power of 2.5 W, an emission interval of 300 milliseconds, and a pulse duration of 100 milliseconds. After activation commences, circular movements will be performed for 30 seconds together with the movement of removing the laser fiber. After the first activation, there will be a 30-second pause and a new 30-second activation cycle will be performed in the same way as the previous one. At the end of LA therapy with ICG, the root canals will be irrigated with 5 ml of saline solution and dried with absorbent paper cones (Dentsply Maillefer, Ballaigues, Switzerland).

Tooth extraction and histotechnical processing

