After the previous procedure, an incision will be made in the gingival tissue around the tooth to be extracted, which will be gently moved away to expose the tooth neck. Then, with an atraumatic extraction kit, the dental element will be dislocated and, using forceps and/or an extractor, the element will be removed. Finally, a suture will be placed to bring the edges of the gingival tissue around the socket as close as possible.

From the dental element, the apical part of the element will be obtained together with the periodontal ligament, which will be immediately placed in individual bottles duly identified, containing 10% formalin solution, buffered with neutral pH, and stored for the first 20 hours and then washed in running water for another 12 hours to remove the fixing solution. After fixation, the pieces will be demineralized in a 10% EDTA solution28. Then, the pieces will be washed in running water, dehydrated in alcohol, cleared in xylene and embedded in paraffin. After inclusion, the pieces will be cut with semi-serial cuts, 3 µm thick, carried out using a microtome (Leica - RM 2045). For each specimen, 5 slides with 3 tissue sections will be prepared and stained with Hematoxylin-Eosin and Picrosirius red29.

Analysis of histological results

Analyzes will be performed at 400x magnification under light microscopy (DM 4000 B, Leica, Wetzlar, Germany) by a single, calibrated, and blinded operator. Histological analysis will be used to characterize the morphological structures of the periodontal ligament with the aim of identifying possible pathological changes. The results will be presented through descriptive and qualitative analysis. The analysis will consider: inflammatory infiltrate in terms of its intensity and extent; periodontal ligament organization; collagen fibers maturation; inflammatory and/or replacement resorption; and dental ankylosis. The two teeth used as controls will serve as baseline parameters to analyze possible morphological changes.

The inflammatory reaction will be scored according to the average number of inflammatory cells present in the middle third of the root of the teeth, being: Score 0, no or few cells (normal); Score 1, <25 cells (mild); Score 2, 25-125 cells (moderate); Score 3, >125 cells (severe).

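### If laser and extraction share one session, as the protocol reads, resorption and ankylosis scores say little or nothing about laser damage, and the plan does not prevent their absence being read as safety

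*Combined protocol and SAP*

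**What the plan says.** The Indication Studied asserts that adding the laser step carries no risk of harm, through heating, to structures outside the treated root.

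The section Laser Ablation Protocol ends when "the root canals will be irrigated with 5 ml of saline solution and dried with absorbent paper cones". The next section, Tooth extraction and histotechnical processing, opens: "After the previous procedure, an incision will be made in the gingival tissue around the tooth to be extracted". The apical portion of the tooth with its ligament is then taken, "which will be immediately placed in individual bottles duly identified, containing 10% formalin solution".

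Analysis of histological results lists inflammatory infiltrate, ligament organization, and "collagen fibers maturation; inflammatory and/or replacement resorption; and dental ankylosis". Resorption and ankylosis are scored from 0 (absent) to 3 by the area affected. Two statements govern how the findings are read: "The results will be presented through descriptive and qualitative analysis" and "The two teeth used as controls will serve as baseline parameters to analyze possible morphological changes".

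The Statistical Analysis Plan applies Shapiro-Wilk and then Mann-Whitney or Student t between Control and Treatment at 5%. It names no endpoint and excludes none.

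**The concern.** A score of 0 supports a no-damage claim only if an injured tooth would have had a fair chance of scoring above 0 when it was examined. Resorption and ankylosis are processes that develop. If the tooth is removed minutes after the laser step, their absence may show only that there was no time for them to appear.

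The reverse also matters. The exclusion criteria in Study design and population do not remove teeth that already have resorption or ankylosis, so a score above 0 may describe the tooth as it arrived.

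Nothing in the plan warns the reader of either point. A table of zeros, or a non-significant comparison, could therefore be offered as support for the claim in the Indication Studied.

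**Working it through.** The documents give no power calculation, margin or interval, so there is no figure of the plan's own to reproduce. The check is mainly of the text, with some supporting arithmetic.

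**1. Is the interval stated?** No. The sequence is anaesthesia (described once), canal preparation, irrigation, laser, rinse, drying, incision, extraction. No canal closure, second visit, recall or second anaesthesia appears before the extraction. The only timed steps from first laser activation are 30 s + 30 s pause + 30 s = 90 s. The adverb of immediacy in the extraction section governs placement in formalin, not the time from laser to extraction. The study dates, 1 August to 30 September 2023, span 30 + 30 = 60 days. They set an outer limit and do not rule out a delay. One session is thus a well-supported inference, not a stated fact.

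**2. What does Score 0 tell us?** Take a tooth with no prior resorption or ankylosis. Let s be the share of laser-injured teeth in which the change is already visible at extraction (an assumption; the documents give no value).

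- P(Score 0 | injured) = 1 − s
- P(Score 0 | not injured) = 1
- Ratio = 1 − s

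At s = 0 the ratio is 1, and Score 0 does not separate a harmless laser from a harmful one. At s = 0.10 the ratio is 0.90, so there is some information but little.

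For ten treated teeth taken as independent, with a share q injured, P(no tooth shows a laser effect) = (1 − q·s)^10. With q = 0.30 assumed:

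| s | P(no tooth shows it) |
|---|---|
| 0 | 1.000 |
| 0.05 | 0.860 |
| 0.10 | 0.737 |
| 0.50 | 0.197 |
| 1 | 0.028 |

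Only the ten comes from the protocol. The table shows how far the reading depends on s; it does not measure the size of the problem.

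**3. Would the group comparison rescue the inference?** With 10 treated and 2 control teeth there are C(12,2) = 66 arrangements. If all 12 teeth score 0, Mann-Whitney gives p = 1 and the t-test is undefined (zero variance). Suppose both controls score 0 and k treated teeth score 1:

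- k = 9: exact two-sided p = C(3,2)/66 = 3/66 = 0.045
- k = 8: exact two-sided p = C(4,2)/66 = 6/66 = 0.091 (0.049 by the normal approximation with continuity correction)

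So eight or nine of ten treated teeth must be affected before the test reaches 5%, depending on which version the software uses. On a one-session reading with small s, a non-significant result is close to assured.

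**4. Would descriptive reporting rescue it?** No. Even at s = 1, zero of ten gives a one-sided 95% upper bound of 1 − 0.05^(1/10) = 25.9% on the injury rate. Dividing by s gives 51.8% at s = 0.5. At s = 0.25 the quotient is 0.2589/0.25 = 1.04, so the bound is 100% and nothing is learned about the eventual rate.

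**The case against.** Four points deserve weight.

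- **The decisive premise is not in the documents.** They give neither the interval nor any latency for resorption or ankylosis. This stands, and it is why the point is conditional and held with medium confidence. It does not remove the need to state the interval: Score 0 cannot be interpreted without it under any latency.
- **The plan does not say that these scores will be tested.** The SAP names no endpoint, and the protocol plans descriptive, qualitative presentation. This stands. A reader might infer a commitment to test resorption and ankylosis; the text shows only that nothing excludes them. Taking them out of the test would not cure the problem either, because a descriptive finding of absence invites the same conclusion.
- **Ten teeth against two would not support a no-risk claim at any interval.** The 25.9% bound and the eight-or-nine-of-ten threshold bear this out. Sample size is a separate weakness, and timing adds to it.
- **Other features are not clearly free of the timing problem.** Infiltrate and collagen maturation may also need time. It would be wrong to treat them as dependable immediate markers that could replace the two features at issue.

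A reader might also infer that the resorption and ankylosis scores carry no information whatever in either direction. That follows only if none of these changes can be visible at extraction (s = 0), which the documents do not establish.

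**Conclusion.** The point holds in conditional form and should be fixed. The protocol reads as laser and extraction in one session but does not say so. On that reading, and assuming that resorption and ankylosis need longer than one appointment to become visible, Score 0 is expected in a previously unaffected tooth regardless of laser injury, and a score of 1 to 3 mainly reflects prior condition. These scores then say little or nothing about the no-damage claim. Neither a non-significant comparison nor a descriptive absence would be evidence for it, and the plan contains no wording that prevents that use.

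No numerical size can be attached. The (1 − q·s)^10 values illustrate an assumption and should not be cited as the size of the problem.

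**What to change.** Leave the clinical schedule unchanged and amend the wording.

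(a) State the laser-to-extraction interval in the protocol and record it for each tooth.

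(b) If it is a single session, say in the SAP that resorption and ankylosis are reported descriptively as the condition at extraction, outside the Control versus Treatment comparison, and not as evidence of laser safety.

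(c) Limit the conclusion to immediate histological change observed at extraction, and state that delayed inflammation, resorption and ankylosis were not assessed.

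(d) Apply the same timing caveat to inflammatory infiltrate and collagen maturation. Before relying on infiltrate, reconcile its scoring region (the middle third of the root) with the retained specimen (the apical portion).

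The cost is text in the protocol, SAP and conclusion, plus one recorded time per tooth; teeth, slides and stains stay the same. The downside is a narrower claim, still read against only two control teeth whose canal preparation the documents do not describe.

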Histopathological Evaluation of the Periodontal Ligament and Cementum of Extracted Teeth Subjected to Laser Ablation with Indocyanine Green

Device Investigated: Leonardo Diode Laser with the LEAP Laser Absorption Solution

Indication Studied: Pulpectomy. Specifically, a laser ablation step facilitated with the LEAP solution, added to the standard procedure for tooth pulpectomy, does not present a risk of damage to tissues and structures external of the treated root as a consequence of possible temperature increases.

Sponsor: CAO Group, Inc.

Protocol ID: 70009423.2.0000.5539

Development Phase: Performance Validation

NCT ID: Not Yet Assigned

Anticipated Initiation Date: 1 August 2023

Anticipated Completion Date: 30 September 2023

Document Date: 10 July 2023

DATA COLLECTION INSTRUMENT

Clinical Procedures and Sample Collection

Study design and population

The patients will be treated at the Unicesumar Dental Clinic. Ten healthy female and male patients, over 18 years old, and in need of tooth extraction, will be selected for the study. Patient selection will be carried out through anamnesis and clinical/imaginological examinations. The inclusion criterion are: lower incisors with indication for extraction.

The exclusion criteria are: other dental groups; teeth that have periodontal disease beyond the apical third of the root; and teeth that do not require tooth extraction.

At least ten teeth will be included in this study for the treatment group, and two other teeth will be used as a control group. The study is porposed under submission to the Human Research Ethics Committee (CAAE 70009423.2.0000.5539) and all patients who agreed to participate in the research will sign the Informed Consent Form.

Endodontic treatment procedure

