For the periodontal ligament organization analysis, the percentage of organization will be considered, where: Score 0, total organization (100%), Score 1, organization greater than 75% and less than 100%; Score 2, greater than 50% and less than 75%; and Score 3, organization of less than 50%.

Inflammatory and/or replacement resorption and dental ankylosis will be considered according to their intensity and extent, where: Score 0, absent, without the presence of the mentioned events; Score 1, change in an area less than 25%; Score 2, change in an area greater than 25% and less than 50%; Score 3, change in an area greater than 50%.

Statistical Analysis Plan

All statistical analysis will be performed using SigmaPlot 12.0[™] software (Chicago, IL, USA). The data obtained will be submitted to the Shapiro-Wilk normality test. Then, for comparisons between the Control and Treatment group, the Mann-Whitney U test will be used for nonparametric data. For parametric data, the Student t-test will be used. The level of significance will be set at 5%.

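### The SAP does not name the unit of analysis or say how about 15 sections become one score per tooth, and its tests are unreliable on 10 v 2 tied tooth scores

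*Combined protocol and SAP*

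**What the plan says.** Group sizes are given in teeth (Study design and population). For treatment: "At least ten teeth will be included in this study for the treatment group". For controls, the wording is: "two other teeth will be used as a control group". The number of patients is ten: "Ten healthy female and male patients, over 18 years old, and in need of tooth extraction, will be selected for the study".

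Under Tooth extraction and histotechnical processing, "For each specimen, 5 slides with 3 tissue sections will be prepared", and the material is "stained with Hematoxylin-Eosin and Picrosirius red". The split of slides between the two stains is not stated.

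Under Analysis of histological results, only one outcome mentions an average: "The inflammatory reaction will be scored according to the average number of inflammatory cells present in the middle third of the root of the teeth". Whether the average runs over fields, sections or slides is not stated. For the ligament, "For the periodontal ligament organization analysis, the percentage of organization will be considered", with no rule for combining sections. Resorption and ankylosis are graded 0-3 by area affected, again with no such rule.

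The Statistical Analysis Plan says "The data obtained will be submitted to the Shapiro-Wilk normality test". It then uses Mann-Whitney U or Student t between Control and Treatment at the 5% level. It names no unit of analysis and makes no allowance for sections within teeth or teeth within patients.

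**The concern.** Mann-Whitney and Student t both assume independent observations. Semi-serial cuts from one root share the same tooth, patient and extraction, so they are repeated measures. Nothing in the SAP stops an analyst from entering 150 treated and 30 control sections as if they were 180 independent results. Two control teeth would then count as 30 observations, and one atypical control tooth would supply half of the control data. A chance difference between teeth could be reported as a laser effect in either direction.

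Even an analyst who works by tooth must decide how 15 scores become one. Mean, median, worst section and a representative section can give different answers, and the plan leaves that choice open until the data have been seen. The study is meant to support a claim that tissue outside the root is not harmed, so both the summary and the test affect how the result is read.

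**Working it through.** The documents contain no sample-size, power or correlation figure, so there is no stated number to reproduce. The benchmark is the nominal 5% level, taken as two-sided (an assumption; sidedness is not stated).

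**Inputs**
- From the documents: 10 treated and 2 control teeth; 5 × 3 = 15 sections per tooth, so 150 v 30.
- Assumed: within-tooth correlation ρ of 0.2, 0.5 or 0.8 (on the underlying continuous scale for ordinal scores).
- Assumed variant: 7 sections per tooth, if each score is read on one stain only.
- Assumed variant: 95% of scores zero. Extraction follows the laser step in the same sequence, so mostly-zero resorption and ankylosis scores are plausible.

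**Sections treated as independent: closed form**

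Design effect D = 1 + (m − 1)ρ, and actual error = 2 × [1 − Φ(1.96/√D)].

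| Sections m | ρ | D | 1.96/√D | Actual error |
|---|---|---|---|---|
| 15 | 0.2 | 3.8 | 1.01 | 31% |
| 15 | 0.5 | 8.0 | 0.69 | 49% |
| 15 | 0.8 | 12.2 | 0.56 | 57% |
| 7 | 0.2 | 2.2 | 1.32 | 19% |
| 7 | 0.5 | 4.0 | 0.98 | 33% |
| 7 | 0.8 | 5.8 | 0.81 | 42% |

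At ρ = 0.5 the 180 sections carry the information of 180/8 = 22.5 independent ones.

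**Sections treated as independent: simulation**

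No true group difference, 0-3 scores, asymptotic Mann-Whitney on pooled sections, 4000 trials per setting.
- Check at ρ = 0 with 15 evenly spread scores: about 5%, as it should be.
- 15 sections, scores evenly spread: about 30%, 50% and 59% at ρ = 0.2, 0.5 and 0.8.
- 7 sections, scores evenly spread: about 17% at ρ = 0.2, rising to about 42% at 0.8.
- 15 sections, 95% of scores zero: about 8-9% at ρ = 0.2, rising to about 22% at 0.8.

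**One value per tooth, 10 v 2**
- On continuous tooth means the t-test holds at about 5%. With nearly all-zero scores it drifts to about 5-10%.
- Exact Mann-Whitney without ties: there are C(12,2) = 66 ways to choose the two control teeth. Complete separation gives two-sided p = 2/66 = 0.030. The next possible value is 4/66 = 0.061, so the true error rate is 3.0%.
- Shapiro-Wilk needs at least three values, so it cannot be run within the two-tooth control group.

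**Tied scores: ten treated teeth at 0, controls at 0 and 1**
- t-test: mean difference 0.5; within-group sum of squares 0.5 on 10 degrees of freedom, so s² = 0.05. SE = √[0.05 × (1/10 + 1/2)] = 0.173; t = 2.89; p = 0.016.
- Asymptotic Mann-Whitney: the 11 zeros share rank 6 and the affected tooth has rank 12. Control rank sum is 18, so U = 18 − 3 = 15 against an expected 10. Tie-corrected variance = (20/12) × [13 − (11³ − 11)/(12 × 11)] = (20/12) × 3 = 5. With continuity correction z = 4.5/√5 = 2.01; p = 0.044.
- Exact: the one affected tooth falls among the two controls with probability 2/12, so p = 0.167.

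Two of the three methods call this significant, although one tooth in twelve is affected and chance puts it in the control group one time in six.

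**The case against.** The strongest reply is that the plan never says sections will be tested. Group sizes are given in teeth, the two control teeth are described as the baseline, and 15 sections can be read as a slide-preparation detail. That stands: section-level testing is left open, not specified. But group sizes in teeth do not tell the analyst how to get from 15 readings to one.

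A reader might also infer that the Shapiro-Wilk step forces sections to be the data, since it cannot run on two control teeth. The documents do not support this. The SAP does not say the check is done per group; it would run on 12 pooled tooth values, and slide-level values (5 × 2 = 10 for controls) would also run per group.

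A reader might further take 30-60% as this trial's false-positive rate. It is not. It needs section-level testing, all 15 sections scored for the outcome although two stains share the slides, well-spread scores, and a correlation that the documents do not give.

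Finally, the protocol says the results will be presented descriptively and qualitatively, and no decision rule depends on a p-value. This lowers the stakes, but the SAP still specifies between-group tests at 5%, so p-values will be produced and read.

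**Conclusion.** The concern holds as a gap in specification. The unit of analysis is unnamed, and three scores have no reduction to one value per tooth. The inflammatory score has an average whose scope is undefined.

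If sections were tested as independent, the 5% error rate would become about 30-60%, 17-42% or 8-22%, depending on the number of sections scored and the spread of scores. All three ranges rest on an assumed within-tooth correlation of 0.2-0.8. In every one of them the error is above nominal.

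Naming the tooth as the unit is not enough by itself. At 10 v 2 with ties, the asymptotic Mann-Whitney and the t-test can each turn one affected control tooth into a significant result, and a per-group normality check is impossible for the controls. These last points do not depend on the assumed correlation.

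**What to change.** Add to the Statistical Analysis Plan, before any slide is read:

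- The tooth is the unit of analysis, and sections are never entered as separate observations.
- For each outcome, the readable sections are reduced to one value per tooth before any test: the mean section score, or the mean percentage of area affected. For inflammatory cells, state what is averaged.
- The worst section per tooth is reported descriptively. The median should not be used: with 7 of 15 sections showing resorption, the median score is still 0, so focal damage would disappear.
- State how teeth from the same patient are handled, since ten patients are to supply at least twelve teeth.
- Replace the normality-gated choice of test with an exact rank (permutation) test on the tooth values.

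The change is to SAP wording and method only; no extra teeth or slides are needed. The downside must be stated openly: with 10 v 2 and no ties the smallest two-sided exact p is 0.030, reached only when the groups separate completely. Larger p-values make a finding of no difference easier to reach, so the SAP should say that a non-significant result is not evidence of no damage. This change does not cure the lack of information in two control teeth.

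### None of the three score rules is a specific sign of heat injury, the collagen reading has no score and no laser-to-extraction interval is stated, so the scores bear only weakly on the temperature claim

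*Combined protocol and SAP*

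**What the plan says.** **The question.** The Indication Studied entry says that the added laser step "does not present a risk of damage to tissues and structures external of the treated root as a consequence of possible temperature increases". The title names two tissues: "Histopathological Evaluation of the Periodontal Ligament and Cementum of Extracted Teeth Subjected to Laser Ablation with Indocyanine Green".

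**The features.** The section Analysis of histological results lists "inflammatory infiltrate in terms of its intensity and extent; periodontal ligament organization; collagen fibers maturation; inflammatory and/or replacement resorption; and dental ankylosis".

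**The score rules.** There are three, each graded 0 to 3:
- Inflammation: "The inflammatory reaction will be scored according to the average number of inflammatory cells present in the middle third of the root of the teeth".
- Ligament: "For the periodontal ligament organization analysis, the percentage of organization will be considered". Score 0 is reserved for complete organisation.
- Resorption and ankylosis share one rule based on area: "Inflammatory and/or replacement resorption and dental ankylosis will be considered according to their intensity and extent".

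**The material.** For each specimen, "5 slides with 3 tissue sections will be prepared and stained with Hematoxylin-Eosin and Picrosirius red". Reading is by light microscopy at 400x by one calibrated, blinded operator. Polarised light is not mentioned.

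**Other relevant text.** The same section plans an unscored qualitative description that looks for pathological change, with the two control teeth as the baseline. The section Tooth extraction and histotechnical processing puts extraction directly after the laser procedure and gives no interval. The Statistical Analysis Plan compares Control and Treatment by Mann-Whitney U or Student t at 5%.

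**The concern.** The harm to be excluded is defined by its cause, a rise in temperature. The outcomes that will be graded are general signs of periodontal reaction and repair. No rule names coagulated or homogenised collagen, lost or shrunken nuclei, necrosis or vessel coagulation, and no temperature measurement is planned. Collagen is stained for, but the listed attribute is its maturation, and nothing says how that is to be graded.

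If the teeth are removed straight after the laser, low scores for inflammation, resorption and ankylosis may show only that these reactions had no time to develop. At stake is how a favourable result can be read: low scores on most scales could coexist with acute heat change, and a reader could take them as support for the temperature claim.

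**Working it through.** The plan gives no figure to reproduce on this point. The check sets the listed features against the score rules and then asks which rules could respond.

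**Step 1. Features against rules** (all from Analysis of histological results)

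| Listed feature | Score rule | Rule names a heat sign? |
|---|---|---|
| Inflammatory infiltrate | Yes, cell count | No |
| Ligament organisation | Yes, percent organised | No |
| Collagen fibre maturation | None | Not applicable |
| Resorption | Yes, area (shared rule) | No |
| Ankylosis | Yes, area (shared rule) | No |

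Features listed: 5. Features scored: 5 − 1 = 4. Distinct rules: 3, because resorption and ankylosis share one. Rules naming a heat sign: 0 of 3. Cementum is in the title but has no heat item of its own.

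**Step 2. Which rules could respond to acute heat change?** The documents do not settle this. The assumption, from general pathology, is that infiltrate, resorption and ankylosis take hours to weeks to develop, while direct heat change is present at once. Because no interval is stated, the answer is given as a range:

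| Laser-to-extraction interval (assumed) | Rules that could respond | Rules specific to heat |
|---|---|---|
| Extraction follows directly | 1 of 3 (organisation) | 0 of 3 |
| Long enough for infiltrate only | 2 of 3 | 0 of 3 |
| Long enough for resorption and ankylosis too | 3 of 3 | 0 of 3 |

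The first row fits the protocol's sequence best. There, 3 − 1 = 2 of 3 rules, covering 4 − 1 = 3 of 4 scored features, could read 0 in heat-injured tissue.

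**Step 3. What is left in the first row?**
- The organisation score. It leaves 0 with any disorganisation, so it may well move. But the tooth is dislocated and pulled with forceps or an extractor, which could also disorganise the ligament, so a raised score could not be assigned to heat.
- The qualitative reading. It could describe heat change, but it has no checklist or grade. Silence on coagulation could mean that it was absent or that it was not looked for.

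**The case against.** **The qualitative reading would catch it.** A calibrated, blinded operator asked to look for pathological change on H&E and picrosirius red may well report coagulated tissue. This stands in part. It rules out saying that the plan is blind to heat injury. It does not give that reading a definition or a grade to compare between groups.

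**The organisation score would catch it.** This also stands in part. Since only complete organisation scores 0, coagulated ligament could plausibly score higher. A reader might infer that a coagulated ligament would score low throughout; the documents do not support that. The defect is lack of specificity.

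**The real fault is timing.** Largely fair. With a longer interval, the inflammation, resorption and ankylosis scores could register the consequences of heating, so the missing interval is part of this point. Stating it would still not supply a heat-specific item or a collagen score.

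**The collagen data may be analysed anyway.** The Statistical Analysis Plan tests the data obtained, without limiting them to the three rules, and the staining step cites a source not available here. So the collagen reading is undefined rather than excluded. A reader might infer that it can never enter the group comparison; the text does not say so.

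**The argument rests on outside histology.** True of Step 2, which is why it is labelled an assumption and shown as a range. Step 1 needs no such assumption.

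**Ten teeth against two cannot establish safety whatever is scored.** A separate limit: 0 of 10 affected leaves a one-sided 95% upper limit of 1 − 0.05^(1/10) = 25.9%. It gives more reason to read each tooth for the relevant sign.

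**Conclusion.** The point holds in a limited form. From the documents alone, 0 of 3 score rules is a specific sign of heat injury, and 1 of 5 listed features, the only one read on collagen, has no score. Under the stated assumption about timing, and if extraction follows the laser directly, 2 of 3 rules (3 of 4 scored features) say little about acute heat damage. Only a non-specific organisation score and an unscored description remain.

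A reader might go further and conclude that the trial cannot answer its objective. The documents do not support that, because those two remaining readings could show heat change. What they support is that low scores on most scales would be weak evidence for the temperature claim. The plan should be changed before any slide is read. Confidence is medium, because the timing step rests on general pathology and the interval is unknown.

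**What to change.** Keep all listed features and make these changes before slides are read:

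1. **Add a thermal-injury score for periodontal ligament and for cementum**, on the slides already cut, read by the same blinded operator. Record the percent of area with homogenised or coagulated collagen, or with pyknotic or absent nuclei. Use H&E as the main basis and picrosirius red as support; use birefringence only if polarised light is available. Grade 0 = none, 1 = >0 to <25%, 2 = 25 to 50%, 3 = >50%.
2. **Compare it with the control teeth** and report it as the item that bears directly on the temperature claim, with the other scores alongside.
3. **Define how the collagen reading is scored**, including how picrosirius red is read.
4. **State the laser-to-extraction interval**, so that the inflammation, resorption and ankylosis scores are interpreted in its light. No particular interval is proposed here.

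The cost is protocol wording and slightly more reading time; no new specimens, stains or staff are needed. The new item may also pick up extraction or processing artefact. The control teeth help to judge that, though with two of them the help is limited.
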